6.8.3.1.1 Recombinant Human Erythropoietin and Derivates

Recombinant human erythropoietin (EPO) is not allowed throughout the entire duration of the study.

Preclinical and clinical studies showed that autocrine or paracrine erythropoietin signaling can enhance cancer invasion in SCCHN and negatively affects patient outcome in terms of OS and local-regional PFS ([Henke 2003](#), [Lambin 2009](#)).

6.8.3.1.2 Food and Herbal Preparations

- Grapefruit juice and grapefruit-containing products (P-gp inhibitors) may lead to increased xevinapant exposure.
- St John's Wort (i.e *Hypericum perforatum*, *millepertuis*) and St John's Wort-containing products (P-gp inducers) may lead to decreased xevinapant exposure.

6.8.3.1.3 Inhibitors/Inducers of P-gp

The concomitant intake of strong inhibitors/inducers of P-gp is prohibited because they may have an impact on the PK disposition of xevinapant (i.e. increase the xevinapant exposure for inhibitors and decrease the xevinapant exposure for inducers). Commonly used drugs are listed below ([Table 12](#)). Please note that this is not an exhaustive listing; refer to the label of potential comedication to verify they are not strong inhibitors/inducers of P-gp.

Table 12 Examples of Prohibited Inhibitors and Inducers of P-gp with Xevinapant

International Nonproprietary Name	
Inhibitors	
Amiodarone ^a	Propafenone
Carvedilol	Quinidine
Clarithromycin	Ranolazine
Dronedarone	Ritonavir
Itraconazole	Saquinavir and ritonavir
Lansoprazole	Telaprevir
Lapatinib	Tipranavir and ritonavir
Lopinavir and ritonavir	Verapamil
Inducers	
Apalutamide	Mitotane
Bosentan	Phenobarbital
Carbamazepine	Phenytoin
Efavirenz	Primidone
Enzalutamide	Rifampin
Etravirine	St. John's wort

Source: <https://www.fda.gov/drugs/drug-interactions-labeling/drug-development-and-drug-interactions-table-substrates-inhibitors-and-inducers> (accessed 16 March 2022).

a. Participants who had long-term use of amiodarone (\leq 6 month) prior to the start of study intervention need to be closely monitored due to the long half-life of this drug with chronic dosing.

6.8.3.1.4 CYP3A4/5 Narrow Therapeutic Index Drugs or Sensitive Substrates

Xevinapant is a strong CYP3A4/5 inhibitor. The drugs listed below should not be coadministered with strong CYP3A4/5 inhibitors. Indeed, there is a risk of clinically significant increased toxicity when the active drug is metabolized by CYP3A4/5 or a risk of decreased efficacy of the concomitant medication when the prodrug is metabolized into the active drug. Commonly used drugs are listed below (Table 13). Please note that this is not an exhaustive listing; refer to label recommendations for other drugs that are low therapeutic index drugs or sensitive substrates of CYP3A.

Table 13 Examples of Prohibited CYP3A4/5 Sensitive Substrates with Xevinapant

International Nonproprietary Name	
Avanafil	Lurasidone
Budesonide	Maraviroc
Buspirone	Midazolam
Conivaptan	Naloxegol
Darifenacin	Nisoldipine
Darunavir	Quetiapine
Dasatinib	Saquinavir
Dronedarone	Sildenafil
Ebastine	Simvastatin
Eletriptan	Sirolimus
Eplerenone	Tacrolimus
Everolimus	Ticagrelor
Felodipine	Tipranavir
Ibrutinib	Tolvaptan
Indinavir	Triazolam
Lomitapide	Vardenafil
Lovastatin	

Source: <https://www.fda.gov/drugs/drug-interactions-labeling/drug-development-and-drug-interactions-table-substrates-inhibitors-and-inducers> (accessed 16 March 2022).

6.8.3.1.5 Prohibited or Concomitant Use of Traditional Chinese Medicines

Any traditional Chinese medication with approval for use as anticancer treatment (regardless of the type of cancer) will not be permitted during study intervention. Traditional Chinese medicines for indications other than anticancer treatment, such as supportive care, may be administered at the discretion of the Investigator. Any traditional Chinese medicines or herbal supplement, if known to be strong inhibitors/inducers of CYP3A4 or inhibitors of P-gp, will not be permitted. Use of traditional Chinese medicines as part of next line of anticancer treatment should be documented as such.

6.8.3.2 Prohibited Medications and Medications to be Used with Caution with Cisplatin or Carboplatin

Prohibited medications

Platinum-based cytotoxic agents may reduce the digestive absorption of phenytoin and fosphenytoin, resulting in reduced epilepsy control and risk of exacerbation of convulsions. Therefore, both phenytoin, and fosphenytoin are prohibited during the combination therapy period.

Granulocyte-Colony Stimulating Factors (G-CSF) are not allowed throughout the screening period and for prophylaxis. Nevertheless, for participants presenting with febrile neutropenia who have

risk factors for infection-related complications or poor clinical outcome, therapeutic G-CSF including secondary prophylaxis should be considered (Becker 2020). Features associated with poor outcome include age > 65 years; sepsis syndrome; ANC < 100 neutrophils/m³; anticipated prolonged (> 10 days) neutropenia, pneumonia, or other clinically documented infection; invasive fungal infections; and hospitalization at the time of fever.

Please also refer to the local product information for cisplatin or carboplatin, as applicable.

Medications to be used with caution

Please consult and follow the instructions provided in your local label.

6.8.4 Other Interventions

6.8.4.1 Nutritional Support

All participants must be screened for nutritional risk and need of early enteral nutrition. Nutrition status must be evaluated as indicated in [Table 1](#), [Table 2](#), and

[Table 3](#).

Maintaining adequate nutritional support is essential during the radiotherapy and monotherapy period. Participants must receive dietary advice to help maintain their weight during the course of radiotherapy. In case of important swallowing difficulties and/or weight loss exceeding 5% to 10%, a feeding tube is recommended, either a percutaneous endoscopic gastrostomy or nasogastric tube can be placed. The Investigator needs to ensure that the participant has access to nutritional support.

A feeding tube is mandatory if the participant has Grade ≥ 3 dysphagia.

6.8.4.2 Dental Care

Participants with head and neck cancers are at risk of oral and dental complications after RT because of treatment-induced xerostomia and salivary gland dysfunction, which are associated with increased dental caries.

In addition, RT to the dental hard tissues is associated with bone demineralization and trismus of the masticatory muscles. Using IMRT and limiting the RT dose to the teeth have been shown to decrease both xerostomia and damage to the teeth (NCCN v1 2023). Dental / oral evaluation and management can help decrease dental caries and associated problems such as dentoalveolar infection and osteoradionecrosis.

The recommended dental / oral evaluations before, during, and after RT are summarized in [Appendix 9](#).

6.8.4.3 Pain

The management of pain should be done according to severity and recommended drugs as per institutional guidelines. Review [Table 10](#) before using concomitant medications.

7 Discontinuation of Study Intervention and Participant Discontinuation/Withdrawal

Discontinuation of specific sites or of the entire study is specified in [Appendix 5](#).

7.1 Discontinuation of Study Intervention

Study intervention (i.e. xevinapant, cisplatin, and IMRT) must be discontinued under the following circumstances:

- Disease progression, including clinical progression as judged by the Investigator, treatment failure, local, or distant relapse, second cancers, or start of any new anticancer treatment including salvage surgery.
- Participant withdrawal of consent for treatment.
- Participants may voluntarily discontinue one or several of the study interventions at any time. If such discontinuation occurs, every effort should be made by the Investigator to determine the primary/underlying reason for this decision, which should be recorded in the eCRF. The participant should be encouraged to remain on study to be followed for efficacy assessments.
- Unacceptable toxicity/AEs that result in a significant risk to the participant's safety.
- Participants who are removed from study intervention due to AEs must be treated and followed up for these AEs according to standard medical practices.
- Any protocol deviation that results in a significant risk to the participant's safety, only after discussion with Sponsor.
- Noncompliance that is deemed by the Investigator or the Sponsor to compromise participant safety or study integrity.
- Pregnancy (Section [8.3.4](#)).
- Investigator decision in the participant's best interest. The primary reason for this decision (e.g. lack of efficacy, AE) must be recorded in the eCRF.
- Early study termination by the Sponsor, SMC, the Investigator, the IEC/IRB, or the Regulatory Agencies.

The primary reason for study intervention discontinuation must be recorded in the eCRF.

If study intervention is permanently discontinued, the participant will remain in the study to be evaluated for safety and efficacy. The SoA indicates data to be collected at the time of discontinuation of study intervention and follow-up and for any further evaluations that need to be completed (

Table 3- EOT visit).

7.1.3 **Temporary Discontinuation**

See Section 6.5.1.2 (xevinapant), Section 6.5.2.1 (cisplatin), and Section 6.5.3.3 (RT) for further guidance on temporary discontinuation of treatment.

7.1.4 **Rechallenge**

See Section 6.5.1.2 for details on study intervention restart or rechallenge criteria.

7.1.4.1 **Study Intervention Restart or Rechallenge After Liver Stopping Criteria Are Met**

Study intervention restart or rechallenge after liver clinical safety laboratory test stopping criteria are met by any participant in this study are not allowed.

7.2 **Participant Discontinuation/Withdrawal from the Study**

- A participant may discontinue from the study at any time, at their own request or at the discretion of the Investigator for safety, behavioral, compliance, or administrative reasons (e.g. disruption of operations due to natural disasters, interruption of laboratory, or facility accreditation, participant moving to another country, resignation of key staff").
- At the time of study discontinuation, if possible, a discontinuation visit will be conducted, as listed in the SoA. The SoA specifies the data to collect at study discontinuation and follow-up, and any additional evaluations that need to be completed.

- If the participant revokes consent for the study, any data collected up to that point may still be used, but no future data can be generated, and any biological samples collected will be destroyed.
- If a participant requests the destruction of any biological samples still remaining, the Investigator will document this in the site study records and inform the Sponsor. The samples will be destroyed.
- Participants may voluntarily withdraw consent for study participation at any time. If such withdrawal occurs, every effort must be made by the Investigator to determine the primary/underlying reason for this decision which must be recorded as reason in the form in the eCRF i.e. if the underlying reason for the decision is toxicity (e.g. AE) this must be recorded as such and the Investigator has to follow-up with the participant until the AE is resolved.
- Premature discontinuation from the study can also be triggered by:
 - Participant lost to follow-up (Section 7.3)
 - Death
 - Disease progression
 - Early study termination by the Sponsor, SMC, the Investigator, the IEC/IRB, or the Regulatory Agencies
- Should a participant be withdrawn from the study, EOS assessments must be performed prior to any further therapeutic intervention, whenever possible. Results of these assessments must be recorded in the eCRF, together with a description of the reasons for study discontinuation.

Participants who prematurely discontinue, for reasons other than DLT-like events earlier than 5 weeks after start of treatment, may be replaced.

7.3 Lost to Follow-Up

A participant will be considered lost to follow-up if repeatedly failing to return for scheduled visits and is unable to be contacted by the study site.

The following actions will be taken if a participant fails to return to the clinic for a required study visit:

- The site will attempt to contact the participant and reschedule the missed visit as soon as possible, counsel the participant on the importance of maintaining the assigned visit schedule and ascertain if the participant wants to or will continue in the study.
- Before a participant is deemed “lost to follow-up”, the Investigator or designee will make every effort to regain contact with the participant: 1) where possible, make 3 telephone calls; 2) if necessary, send a certified letter (or an equivalent local method) to the participant’s last known mailing address, and 3) if a participant has given the appropriate consent, contact the participant’s general practitioner or caretaker (where allowed by local regulations) for information. These contact attempts will be documented in the participant’s medical record.
- If the participant continues to be unreachable, he/she will be deemed as “lost to follow-up”.

8 Study Assessments and Procedures

- Study assessments and procedures and their timing are summarized in the SoA. It may be necessary to perform these assessments at unscheduled timepoints if deemed clinical necessary by the Investigator.
- **No** protocol waivers or exemptions are allowed.
- Immediate safety concerns are discussed with the Sponsor immediately upon occurrence or awareness to determine if the participant will continue or discontinue study intervention.
- Adherence to the study design requirements, including those specified in the SoA, is essential, and required for study conduct.
- All screening evaluations will be completed and reviewed to confirm that potential participants meet all eligibility criteria. The Investigator will maintain a screening log to record details of all participants screened, to confirm eligibility, and if applicable, record reasons for screening failure.
- Prior to performing any study assessments that are not part of the participant's routine medical care, the Investigator will obtain written informed consent as specified in [Appendix 5](#).
- Procedures conducted as part of the participant's routine medical care and obtained before signing of the ICF may be used for screening or baseline purposes provided the procedures met the protocol-specified criteria, were performed within the time frame defined in the SoA, and if reviewed, and approved by the Sponsor.
- A participant will be allowed to receive study intervention after he/she has signed the ICF, all eligibility criteria have been met, and the IMRT plan has been sent to the RT-QA Review Center (see [Appendix 5](#)). The IMRT plan must have been reviewed by the RT-QA Review Center prior to the start of the IMRT.
- About 250 mL of blood total will be taken throughout the study. Up to 50 mL of blood may be drawn at certain visits. These blood samples will be used for the following purposes: clinical laboratory tests, PK, **CCI** [REDACTED]. The volume of collected blood might increase due to repeat collections that may be necessary.
- Where allowed by local law/regulations, samples collected during this clinical study may be transferred to a biobank and used for future research outside the clinical protocol when additional consent for this purpose is given. Transfer to the biobank will be documented and any testing of coded biobank samples will **not** be reported in the CSR.

Order of Assessments

- ECG readings must be taken prior to blood collection.

Screening Period

Participants will be screened between Days -28 and -1, prior to start of study intervention (Day 1 [-3 days]). Activities and procedures to be performed at Screening are detailed in the SoA (Section [1.3](#)). Screening-specific procedures include:

- Demography: birth year, age at informed consent, sex, race (only where allowed by local law/regulations), and ethnicity.
- Medical history: previous illness and surgeries (e.g. all during the past year and only major ones prior to that), concomitant illness, relevant medication/ therapies, allergies, tobacco use, alcohol use.
- Eastern Cooperative Oncology Group Performance Status: assessed at Screening to assess eligibility (Section 5.1) and then assessed according to the SoA (Section 1.3).
- Disease history and tumor staging (using the AJCC/TNM Staging System, 8th Ed.) based on radiological imaging. Please refer to Section 8.1.1 for further details on radiologic imaging.
- Results from the local laboratory should be used for defining participant eligibility during Screening.
- Dental examination, audiometry (if required), HBV/HCV/HIV tests, fiberoptic endoscopy and ¹⁸F-FDG-PET scan performed within 4 weeks before ICF signature do not have to be repeated during screening.
- Intravenous contrast-enhanced CT scan or MRI of head and neck, and CT scan of chest are only accepted if they are performed within 4 weeks before study intervention starts.
- HPV status by p16 IHC (mandatory for OPC, optional for other tumor locations) does not have to be repeated if performed prior to ICF signature in line with instructions in Section 8.2.4.1.

8.1 Efficacy Assessments and Procedures

Assessment of tumor response to treatment will be assessed locally according to the Response Evaluation Criteria in Solid Tumors (RECIST v1.1) as described in [Appendix 2](#) but will also take into consideration clinical, anatomopathological, and functional assessments of the tumor.

Tumor assessments (clinical and radiological) should be continued until disease progression (as per RECIST v1.1) occurs, next line of anticancer treatment is started, or EOS, whichever occurs first as per SoAs ([Table 1](#), [Table 2](#), and

[Table 3](#)) and are scheduled, after the EOT visit, every 3 months.

Participants who progress (as per RECIST v1.1) or who start next line of anticancer treatment will discontinue the study. If study intervention is permanently discontinued in participants without disease progression according to RECIST v1.1 (e.g. unacceptable toxicity), the participant will remain in the study to be evaluated for safety and efficacy. The SoA indicates data to be collected at the time of discontinuation of study intervention and follow-up and for any further evaluations that need to be completed (

[Table 3](#)-EOT visit). Efficacy assessments will continue to be performed until disease progression, start of next line therapy, or EOS, whichever occurs first.

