Minimum 2 to 3 hours prior to administration of cisplatin	until a minimum of 2 hours after the administration of cisplatin

The EOT visit will be performed 14 days (\pm 7 days) after last study intervention administration (i.e. xevinapant, cisplatin, or IMRT, whichever is administered last) or 14 days (\pm 7 days) after premature discontinuation during treatment but prior to the start of any subsequent anticancer therapy. In case of premature treatment discontinuation, imaging and clinical tumor assessments must be performed according to original schedule (Week 20 for EOT assessment and every 3 months thereafter).

Every attempt should be made to have each participant attend each visit as scheduled. Study visits/procedures performed outside of the allowed visit window will be considered as protocol deviations, with the exception of premature discontinuation from study intervention or withdrawal from the study due to reasons described in Section [7](#).

The follow-up period will start after the EOT visit. The follow-up period must be performed according to the planned visit schedule within the permitted visit windows. Participants without any progression, treatment failure, local, or distant relapse, second cancers, or death will be followed until the last on-study participant reaches their 18-month post-first treatment visit (EOS), or a decision to end the study has been triggered, or until premature discontinuation from study, whichever occurs first. The same is applicable for participants who prematurely discontinue study treatment without disease progression (e.g. unacceptable toxicity). Participants with confirmed disease progression will discontinue the study.

At the EOS, all remaining participants will have an EOS visit unless their last follow-up visit was done less than 6 weeks before.

During the follow-up period, each study visit day and allowed time windows will be based on the C1D1 date.

After completion of the follow-up period, participants who have not discontinued the study prematurely will undergo the EOS assessments ([date of the 18-month visit of the last on-study participant] \pm 1 month) and will be considered as having completed the study (see Section [7.2](#)).

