If the last on-study participant completes the follow-up (18 months after C1D1), their EOS visit will be performed at the same time as their 18-month visit. In case of premature discontinuation from the study including confirmed disease progression, the participant's EOS visit will be performed when they discontinue from the study.

The following schedules of activities and as assessments are presented:

Table 1: Screening

Table 2: Combination Treatment Period (Cycles 1 to 3)

Table 3: Monotherapy Period (Cycles 4 to 6) and FU/EOS Visits

Figure 3: Treatment Diagram and Time Windows for Visits

Table 4: Schedule of Pharmacokinetic Activities

Table 1 Schedule of Activities: Screening

	Screening	Notes
Study Week	-4 to -1	
Study Day	-28 to -1	
Informed consent	X	
Medical history	X	
Demographics	X	
Nutritional status	X	According to institutional standards
Dental examination	X	No repeat needed if performed within 4 weeks prior to ICF signature. See Appendix 9 .
Audiometry	X	No repeat needed if performed within 4 weeks prior to ICF signature. See Section 8.2.7
Eligibility	X	
Physical examination	X	Complete examination
ECOG PS	X	
Vital Signs	X	Including height and weight
ECG	X	
Laboratory assessments		
Blood hematology	X	Local laboratory
Blood biochemistry – full panel	X	Local laboratory
Coagulation	X	Local laboratory
Pregnancy test	X	Local laboratory. hCG serum at Screening and thereafter from urine for POCBP
Urinalysis	X	Local lab
HPV status (p16)	X	Determined by p16 IHC using CCI , see Section 8.2.4.1 . No repeat needed if performed prior to ICF signature in line with instructions in Section 8.2.4 . Mandatory for OPC, optional for other tumor locations. For OPC, CCI may be performed, if necessary.
HBV, HCV, HIV test	X	Local laboratory. No repeat needed if performed within 4 weeks prior to ICF signature
SARS-CoV-2 test	X	If applicable, see exclusion criterion (See Section 5.2)
Disease assessments		
Disease History	X	Including tumor staging
¹⁸ F-FDG-PET	X	No repeat needed if performed within 4 weeks prior to ICF signature
CT or MRI + CT-chest	X	IV contrast-enhanced CT scan or MRI of head and neck AND CT scan of chest
Clinical tumor assessment	X	Ear, nose, and throat examination, and fiberoptic endoscopy. Fiberoptic endoscopy performed within 4 weeks before ICF signature does not have to be repeated during screening
Other clinical assessments		
Concomitant therapy	X	
Adverse events	X	

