8.3 Adverse Events, Serious Adverse Events, and Other Safety Reporting

- The definitions of an AE and SAE are in [Appendix 7](#).
- The Investigator and any qualified designees (e.g. Subinvestigators) are responsible for detecting, documenting, and recording events that meet the definition of an AE or SAE. The Investigator remains responsible for following up all AEs, considered related to the study intervention or study procedures, or that caused the participant to discontinue the study intervention or study, as specified in Section [8.3.2](#).
- Requests for follow-up will usually be made via the Sponsor or CRO-designated study team member, although in exceptional circumstances the global patient safety department may contact the Investigator directly to obtain further information or to discuss the event.
- The method of recording, evaluating, and assessing causality of AEs and SAEs and the procedures for completing and transmitting SAE reports are in [Appendix 7](#)
- All AEs and SAEs will be collected from the signing of the ICF until the EOS/follow-up visit at the timepoints specified in the SoA (Section [1.3](#)). Beyond this reporting period, any new unsolicited SAEs that the Investigator spontaneously reports to the Sponsor will be collected and processed.
- All SAEs will be recorded and reported to the Sponsor or designee immediately and under no circumstance will this exceed 24 hours, as indicated in [Appendix 7](#). The Investigator will submit any updated SAE data to the Sponsor within 24 hours of it being available using the same procedure that was used for the initial report.
- Investigators are not obligated to actively solicit information on AEs or SAEs after the end of study participation. However, if the Investigator learns of any SAE, including a death, at any time after a participant has been discharged from the study, and he/she considers the event to be reasonably related to the study intervention or study participation, the Investigator will promptly notify the Sponsor.

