9.4.2 Safety Analyses

All safety analyses will be performed on the FAS/SAF except for the analysis of the primary endpoint, which will be performed on the DLT analysis set.

Reference #	Statistical Analysis
Primary	
1 – Occurrence of DLT-like events	
DLT-like events are defined in Section 8.2.5.1.
 
All DLT-like events that occurred in the analysis population during the DLT-like assessment period of each participant will be analyzed.
 
The number and proportion of participants experiencing DLT-like events in the analysis population will be reported together with the corresponding Clopper-Pearson 95% CI.

Secondary	
2 – safety	
TEAEs are defined as AEs emerging or worsening after start of treatment until 30 days after end of treatment. Adverse events will be coded according to the latest available version of the Medical Dictionary for Regulatory Activities (MedDRA). Severity of AEs will be graded by the Investigator using the NCI-CTCAE (Version 5) toxicity grades. TRAEs will be defined as any AE considered as related to study treatment. Incidence of TEAEs which includes AESIs and TRAEs summarized by SOC and PT.

Reference #	Statistical Analysis
	
Laboratory results will also be classified by Grade according to NCI-CTCAE. Worst on treatment grades as well as shifts to worst on treatment grades will be summarized. Measurements without NCI-CTCAE grading will be summarized by above, within, and below normal limits.
 
Vital parameters, weight, and ECOG performance status and corresponding changes from baseline will be presented as descriptive statistics by timepoint.
 
Further details will be provided in the Integrated Analysis Plan.

AE=adverse event, AESI=adverse events of special interest, CI=confidence interval, ECOG=Eastern Cooperative Oncology Group, MedDRA=Medical Dictionary for Regulatory Activities, NCI-CTCAE=National Cancer Institute Common Terminology Criteria for Adverse Events, PT=Preferred Term, SOC=System organ class, TEAE=treatment-emergent adverse event, TRAE=treatment-related adverse event.

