When the participant has only nontarget lesions. In this study, it is not a requirement for study entry to have measurable disease. The same general concepts apply here as noted above; however, in this instance there will be no measured disease assessment to balance the interpretation of an increase in non-measurable disease burden. The test that should be applied when assessing participants for unequivocal progression is to consider if the increase in overall disease burden based on the change in non-measurable disease is at least comparable in magnitude to the increase that would be required to declare PD for measurable disease.

- *Evaluation of New Lesions*

The appearance of new malignant lesions denotes disease progression by RECIST v1.1. The finding of a new lesion should be unequivocal: i.e. not attributable to differences in scanning technique, change in imaging modality, or findings thought to represent something other than tumor. A lesion identified on a follow-up study in an anatomical location that was not scanned at baseline is considered a new lesion and will indicate PD. Exceptionally, since the endpoints of this study differentiate between locoregional progression and distant metastasis, it is necessary to differentiate between locoregional lesions and metastases elsewhere. Therefore, data on new lesions in each of these *locations* will be required if available. If the first manifestation of disease progression is distant metastasis, then assessments for locoregional control should continue if possible, and vice versa. Note: As this study is in locally advanced disease, all target and nontarget lesions at baseline will lie within the locoregional volume and therefore no similar differentiation at baseline is possible or required.

If a new lesion is equivocal, either continued therapy and follow-up evaluation or biopsy and histological examination will clarify if it represents truly new disease. If repeat scans or biopsy confirm a new lesion, then PD should be declared using the date of the initial scan.

In case histopathological results of a new lesion unequivocally reveal a non squamous histology of the new malignant lesion, this will not be counted as disease progression within the secondary endpoints of this study.

Evaluation of Disease Status at Each Postbaseline Timepoint

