### **15.3 Deaths, Other Serious Adverse Events, and Other Significant Adverse Events**

#### **15.3.1 Deaths**

All deaths, deaths within 30 days after last dose of study intervention, death within 60 days after first dose as well as reason for death, will be tabulated based on information from the "Death" page in eCRF:

- Number of Deaths
- Number of Deaths within 30 days after last dose of each study intervention
- Number of Deaths within 30 days after last dose of any study intervention
- Number of Deaths within 60 days after first dose of any study intervention
- Primary Reason of Death:
  - Disease progression
  - AE related to study intervention
  - AE not related to study intervention
  - Other
  - Unknown

In addition, date and cause of death will be provided in individual participant data listing together.

This listing will include:

- AEs with fatal outcome (list preferred terms of AEs with outcome=fatal)
- Flag for death within 30 days of last study intervention
- Flag for death within 60 days of first study intervention

Where AE related/not related to study intervention in Primary Reason of Death is defined as patients with:

- Related = 'What is the primary cause of death?' in "Death" page in eCRF is 'Adverse Event' and at least 1 fatal AE related to any study intervention
- Not related = 'What is the primary cause of death?' in "Death" page in eCRF is 'Adverse Event' and no fatal AE related to any study intervention

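### Leaving the study at progression or next-line therapy ends AE and death collection before the 30-day safety windows close for those who leave early

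*Protocol*

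**What the plan says.** **When participation ends.** Protocol 8.1 gives the rule: "Participants who progress (as per RECIST v1.1) or who start next line of anticancer treatment will discontinue the study". Protocol 1.3 says the same for progression only: "Participants with confirmed disease progression will discontinue the study". Section 7.2 also lists progression as a trigger for leaving the study, and wants EOS assessments done before any further therapy where possible. Only 8.1 names next-line therapy as a reason to leave.

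**When safety collection ends.** For a participant who leaves early, the "EOS visit will be performed when they discontinue from the study" (Protocol 1.3). Protocol 8.3 sets the collection period: "All AEs and SAEs will be collected from the signing of the ICF until the EOS/follow-up visit". After participation ends, 8.3 does not oblige investigators to seek AEs or SAEs. A later SAE or death must be notified only if the investigator learns of it and considers it reasonably related.

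**What the analyses use.** Protocol 9.4.2: "TEAEs are defined as AEs emerging or worsening after start of treatment until 30 days after end of treatment". SAP 15.3.1 tabulates "Number of Deaths within 30 days after last dose of any study intervention", and its death listing carries a 30-day flag.

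**Passages that do not fit together.** Protocol 7.1 puts progression first among the reasons to stop treatment, then says: "If study intervention is permanently discontinued, the participant will remain in the study to be evaluated for safety and efficacy". Protocol 8.1 has nearly the same sentence but limits it to participants without RECIST progression. Appendix 2 says that if distant metastasis is the first sign of progression, "then assessments for locoregional control should continue if possible, and vice versa".

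**The concern.** Safety is what this study is for. Participants who progress early are among those most likely to have serious events or die soon after treatment, and they are the ones whose follow-up is cut. They remain in the FAS/SAF denominator. In a single arm with crude proportions, an event that is never collected can only lower the reported figure.

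The timing makes this more than a rare accident. The first scheduled post-baseline tumor assessment is the Week 20 EOT assessment, which for a full course falls inside the 30-day window. The visit most likely to find early progression is thus also one that ends safety collection too soon.

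A second effect concerns secondary endpoint 6, time to subsequent systemic treatment. A participant whose progression comes first leaves before the next therapy starts and is censored at the moment the event becomes likely.

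**Working it through.** **1. Reproduce the plan's visit day.** Inputs: six 3-week cycles with xevinapant on Days 1 to 14 (Protocol 6.5.1); EOT 14 ± 7 days after last administration, shown as Week 20, Day 134 (Table 3).

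- Cycle 6 Day 1 = 1 + 5 × 21 = Day 106, as in Table 3.
- Last planned dose = 106 + 13 = Day 119.
- EOT = 119 + 14 = Day 133, range 126 to 140. The stated Day 134 is the first day of Week 20 (19 × 7 + 1) and lies inside that range.

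**2. Unobserved part of the window.** The 30-day window for a full course ends on 119 + 30 = Day 149.

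| Exit point | Days after last dose | Days of the 30 unobserved |
|---|---|---|
| EOT visit, earliest | 7 | 30 − 7 = 23 |
| EOT visit, nominal | 14 | 30 − 14 = 16 |
| EOT visit, latest | 21 | 30 − 21 = 9 |
| Week 20 scan at Day 134 (± 7), full course | 15 (8 to 22) | 15 (22 to 8) |
| Exit more than 30 days after last dose | > 30 | 0 |

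The 9 to 23 days also apply to a participant who progresses during treatment, attends the EOT visit after premature discontinuation that 1.3 requires, and then leaves.

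**3. Does anything else close the gap?** Table 3 has no contact at 30 days. Protocol 8.3.2 follows SAEs and AESIs already reported; it does not detect new ones. Appendix 7 counts fatal progression as an AE only within the same reporting period. An unrelated or disease-related death on, say, day 25 after last dose has no required route to the database once the participant has left.

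**4. How many participants?** The documents do not say. Assumption: exponential PFS, using the earlier study's figures in Protocol 2.3.2, read at Day 149 (149 / 30.44 = 4.9 months), with the planned 40 treated.

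- From 36-month PFS of 72% (xevinapant arm): rate = −ln(0.72) / 36 = 0.00913 per month; 1 − exp(−0.00913 × 4.9) = 4.4%; 40 × 0.044 = about 2.
- From a median of 16.9 months (placebo arm): rate = ln 2 / 16.9 = 0.0410 per month; 1 − exp(−0.0410 × 4.9) = 18.2%; 40 × 0.182 = about 7.

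Under this assumption these are upper figures for progression. PFS events include deaths, and a participant who stopped treatment early may progress before Day 149 with the window already closed. They do not count next-line therapy started without progression.

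**The case against.** Several stronger readings are tempting, and the documents do not support them.

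- *Time to subsequent therapy cannot be observed.* It can when next-line therapy starts before RECIST progression, because that start is itself an exit trigger, and Table 3 collects antineoplastic therapy at EOT and follow-up. What remains is informative censoring when progression comes first. SAP 14 drops the efficacy analyses, so this touches the protocol endpoint only.
- *All 30 days can be lost.* That would need the EOT visit in 1.3 to be skipped, and 1.3 gives no exemption for progression.
- *Clinical progression on treatment means leaving at once.* Exit under 8.1 requires RECIST progression, 1.3 requires confirmed progression, and Appendix 2 says symptoms alone do not determine progression. Only 7.2 leaves progression unqualified.
- *Section 7.1 flatly contradicts 8.1.* It lacks the qualifier that 8.1 carries. That is a wording conflict to reconcile, and the Appendix 2 instruction applies only where possible.
- *A round share such as 10% to 20% is affected.* No source in the documents supports it.

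There are also real safeguards. Known SAEs and AESIs are followed to resolution or stabilization, related SAEs are notifiable at any time, and unsolicited SAEs are processed. The follow-up AE row in Table 3 has no limit at progression, but a participant who is off study has no follow-up visits. The gap therefore falls mainly on new non-serious or unrelated events and on deaths not judged related. The 5-week primary endpoint is scarcely touched.

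Finally, SAP 7.1 keeps the TEAE tables, deaths by primary reason and the death listing, but does not name the 30-day death count. SAP 9.8, which defines the on-treatment period, is redacted, as are the sections on last contact and follow-up time. Short follow-up may already be reported there.

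**Conclusion.** The point stands for a defined group: participants who meet the exit rule during treatment or within 30 days of last dose, including those found at the Week 20 EOT scan. They can leave with 9 to 23 days of the window unobserved (16 nominal) while counting as fully observed in the denominator. TEAE proportions and 30-day deaths are then biased low.

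The size of that bias cannot be computed, because neither the event rate after exit nor the number leaving is given. The figure of at most about 2 to 7 progressors in 40 rests on exponential PFS, on transferring results from an earlier study with a different cisplatin schedule, and on 40 being treated. SAP 7.1 describes a reduced scope and does not state the number treated. The 30-day TEAE window rests on Protocol 9.4.2.

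**What to change.** **Protocol.** In 1.3, 7.2 and 8.1, keep AE/SAE and vital-status collection through at least 30 days after last study intervention, regardless of progression or new therapy. For a full course that contact falls on Day 149 or later. Record the start date of the first subsequent systemic therapy. Make 7.1 and Appendix 2 agree with these sections on who stays in the study after progression and for which assessments.

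**Synoptic CSR.** A protocol change cannot recover data already locked on 20-SEP-2024. For that report, show the number of participants observed for less than 30 days after last dose beside the TEAE tables and beside the death table and listing.

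**Cost.** Protocol wording, one extra contact for a few participants, and one table row.
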